APPENDIX 3. SAFETY DEFINITIONS AND ASSESSMENTS

Adverse Event (AE)

An AE is defined as any untoward medical occurrence associated with the use of a drug in humans, whether or not considered drug related. An AE can therefore be any unfavorable and unintended sign (including an abnormal laboratory finding, for example), symptom, or disease temporally associated with the use of a medicinal (investigational) product, whether or not related to the medicinal (investigational) products.

Pre-existing diseases or conditions will not be considered AEs unless there is an increase in the frequency or severity, or a change in the quality, of the disease or condition. Worsening of a pre-existing condition is considered an AE.

Any abnormal laboratory test results (hematology, clinical chemistry, or urine) or other safety assessments (eg, vital sign measurements), including those that worsen from Screening/baseline that are felt to be clinically significant in the medical and scientific judgment of the Investigator are to be recorded as AEs.

Treatment-emergent AE (TEAE)

A TEAE is defined as any AE not present prior to the initiation of the drug treatment or any AE already present that worsens in either intensity or frequency following exposure to the drug treatment.

Serious Adverse Event (SAE)

An SAE is an AE that meets any of the following criteria in the view of either the Investigator or Ultragenyx:

- Death
- Life-threatening

A life-threatening AE is an event that places the patient or subject at immediate risk of death. It does not include events that if it had occurred in a more serious or severe form might have caused death. For example, drug induced hepatitis that resolved without evidence of hepatic failure would not be considered life threatening even though drug induced hepatitis can be fatal.

• Inpatient hospitalization or prolongation of existing hospitalization

Hospitalization is defined by Ultragenyx as a full admission to hospital for a period of 24 hours or longer for diagnosis and treatment. This includes prolongation of an existing inpatient hospitalization. Examples of visits to a hospital facility that do not meet the serious criteria for hospitalization include:

- Emergency room visits (that do not result in a full hospital admission)
- Preplanned or elective procedures prior to study enrollment (e.g., outpatient surgery)
- Protocol procedures

Hospitalization signifies that the subject has been detained (usually involving at least an overnight stay) at the hospital or emergency ward for observation and/or treatment that would

not have been appropriate in the physician's office or outpatient setting. When in doubt as to whether 'hospitalization' occurred or was necessary, the AE should be considered serious.

AEs requiring hospitalization should be considered SAEs. Hospitalization planned prior to study enrollment (eg, for elective surgery or routine clinical procedures) that are not the result of AE (e.g., elective surgery for a pre-existing condition that has not worsened) need not be considered AEs or SAEs. If anything untoward is reported during the procedure, that occurrence must be reported as an AE, either 'serious' or 'nonserious' according to seriousness criteria described above.

• Disability/Incapacity

An AE is disabling or incapacitating if it results in substantial and/or permanent disruption of the subject's ability to carry out normal life functions.

- Congenital anomaly/birth defect not present at screening
- Important Medical Events that may not result in death, be immediately life-threatening, or require hospitalization may be considered serious when, based upon appropriate medical judgment, they may jeopardize the patient or subject and may require medical or surgical intervention to prevent one of the criteria listed in the definition. Examples of such events are:

Intensive treatment in an emergency room or at home for allergic bronchospasm

Blood dyscrasias that do not result in inpatient hospitalization

Development of drug dependency or drug abuse

Adverse Events of Special Interest (AESI)

An AESI is one of scientific or medical interest specific to the product (or product class) or program requiring further investigation and ongoing monitoring to better characterize them. Such events can be serious or non-serious and could include events that might be potential precursors or prodromes for more serious medical conditions in susceptible individuals.

Participation-emergent Adverse Events

These events may be related to study participation or biological specimen collection and will be reported by the investigator and noted as such in the case report form (CRF) as related to study intervention.

Overdose

An overdose is defined as a known deliberate or accidental administration of investigational drug, to or by a study subject, at a dose above that which is assigned to that individual subject according to the study protocol. All cases of overdose (with or without associated AEs) will be documented in the CRF. **Assessment of Severity**

The severity or intensity of an AE refers to the extent to which an AE affects the patient's daily activities. The severity of all AEs will be graded using the Common Terminology Criteria for Adverse Events (CTCAE) version 5.0, published on 27 November 2017.

If an AE cannot be graded using the CTCAE criteria, it should be graded using the following definitions:

• Mild (Grade 1): Asymptomatic or mild symptoms; clinical or diagnostic observations only; intervention not indicated.

- Moderate (Grade 2): Minimal, local or noninvasive intervention indicated; limiting ageappropriate instrumental activities of daily living (ADL). Note: Instrumental ADL refer to preparing meals, shopping for groceries or clothes, using the telephone, managing money, etc.
- Severe (Grade 3): Medically significant but not immediately life-threatening; hospitalization or prolongation of hospitalization indicated; disabling; limiting self care ADL. Note: Self care ADL refer to bathing, dressing and undressing, feeding self, using the toilet, taking medications and not bedridden.
- Life-threatening (Grade 4): Urgent intervention indicated.
- Death (Grade 5): Death related to AE.

Note: The term "severe" is often used to describe the intensity (severity) of a specific event (as in mild, moderate, or severe myocardial infarction); the event itself, however, may be of relatively minor medical significance (such as severe headache). This is not the same as "serious" which is based on subject/event outcome or action criteria and is usually associated with events that pose a threat to a subject's life or functioning. Seriousness (not severity) serves as a guide for defining regulatory reporting obligations.

Assessment of Causality

The Investigator will make a causality assessment about the relationship of each AE to study drug. Treatment-related conditions must be distinguished from disease-related conditions.

The Investigator should determine the causality (relation to the study drug) based on his/her clinical experience and on the information given in the Investigator's Brochure. The causal relationship of all AEs to the study drug will be judged as either related (which includes possibly, probably or definitely related) or not related (which includes unlikely or doubtfully related).

To ensure consistency of AE and SAE causality assessments, Investigators should apply the following general guideline:

• A **related** causal relationship means that there is at least a reasonable possibility that the event is caused by the study drug or the research procedures. There may be a reasonable possibility of a causal relationship between study drug/Investigational Product (IP) and the AE when the event:

Follows a reasonable temporal sequence post IP administration

The event is known to be or could be a response to the IP, based upon pre-clinical or clinical data with the product or similar products

The event could not be explained by the subject's primary disease including progression/expression of the disease state, other concurrent or underlying illness, and/or prior/concomitant therapies

Positive dechallenge: the event resolves or improves after discontinuation of IP (when this information is available)

Positive rechallenge: the event reappears or worsens when dosing with IP is resumed after an interruption (when this information is available)

• **Not related** means there is unlikely to be a reasonable possibility of a causal relationship between the event and study drug/IP or the research procedures, and/or that there is a clear causal relationship between other conditions and the AE. There is not likely to be a reasonable possibility of a causal relationship between study drug/IP and the AE when:

The event does not follow a reasonable temporal sequence post IP administration

There are no data with the IP or similar products, suggesting the event occurs or may occur with the IP

There is a more likely alternative etiology, such as subject's underlying primary disease including disease progression or expression, other concurrent or underlying illness, or prior/concomitant therapies

Negative dechallenge: the event does not improve after discontinuation of IP (when this information is available)

Negative rechallenge: the event does not worsen after interruption of IP when dosing is resumed after an interruption (when this information is available)

Note: The Investigator's assessment of causality for individual AEs is part of the study documentation process and will be recorded in the patient's medical record, CRF, and SAE form, if applicable. AEs recorded without the Investigator's assessment of the relationship to study drug will be followed up until causality is assigned.

Suspected Unexpected Serious Adverse Reaction (SUSAR) means an SAE that occurs in a clinical trial subject, which is assessed by the Investigator or Ultragenyx as being serious and unexpected based on Reference Study Information (e.g., Investigators Brochure), and as having a reasonable possibility of a causal relationship with the study drug/IP.

Urgent Safety Measure means any measure taken to protect the subjects of a clinical trial against an immediate hazard to their health or safety.

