11.2.2.2. Tertiary Efficacy Endpoints

11.3. Safety Analyses

Safety variables including all SAEs, TEAEs, AESIs, safety laboratory assessments, anti-setrusumab antibodies, vital signs, ECGs, physical examination, focused neurological examination, audiometry, and dental health assessments will be summarized descriptively and listed by subject.

All AEs will be coded according to the MedDRA Version 24.0 or above. The frequency and severity of all TEAEs, SAEs, AESIs and clinically relevant laboratory and ECG abnormalities reported as AEs will be reported by System Organ Class, Preferred Term, by severity, and by relationship to study drug, if applicable. All non-serious AEs reported with onset after the first dose of study drug (ie, TEAEs) will be included in the analysis. All SAEs will also be reported by relationship to study drug as reported by Investigator, seriousness criteria, timing, duration, and outcome. For all TEAEs; SAEs; AESIs; and treatment-related TEAEs, SAEs, and AESIs; the percentage of subjects who experienced at least 1 occurrence of the given event will be summarized. Data summaries and\or listings, and narratives will be provided for subjects who died, discontinued treatment or withdrew from study due to TEAE, or experienced SAEs, AESIs, and any study procedure-related AEs.

Clinical laboratory data changes from ASTEROID Baseline and Retreatment Baseline will be summarized by the type of laboratory test. Reference ranges and abnormal results (specified in the SAP) will be used in the summary of laboratory and ECG data. The frequency and percentage of subjects who experience abnormal clinical laboratory results (ie, outside of reference ranges) and/or clinically significant abnormalities (as determined by the Investigator) will be presented for each clinical laboratory measurement, including for Hy's Law analysis (alanine transaminase [ALT], aspartate aminotransferase [AST], total and direct bilirubin, alkaline phosphatase). Shift tables will be provided for changes from ASTEROID Baseline and Retreatment Baseline in selected chemistry and hematology laboratory parameters (if applicable). Listings of abnormal vital signs and physical findings will be provided (if applicable).

The SAP will provide additional details on the planned safety analyses.

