A consistent methodology of non-directive questioning for eliciting AEs at all patient evaluation time points should be adopted. Examples of non-directive questions include:

- "Since the last visit, has the patient experienced any health problems?"
- "Have there been any new or changed health problems since you were last here?"

Recording AEs and SAEs

All AEs (ie, any new condition or worsening in severity or frequency of a preexisting condition) experienced by the patient within the protocol defined timeframes must be promptly documented on the case report form (CRF) and SAE form if applicable. For clinically significant worsening of a preexisting condition from Baseline the changes will be documented as AEs on the CRF. Clinical significance is defined as any variation in signs, symptoms, or testing that has medical relevance and may result in an alteration in medical care. The Investigator will continue to monitor the patient until the assessment returns to Baseline or until the Investigator determines that follow-up is no longer medically necessary.

For IP and for non-IP studies, any AEs or SAEs considered associated with study protocol-required procedures will also be collected

The Investigator is responsible for evaluating all AEs, obtaining supporting documents, and ensuring documentation of the events is adequate. Details of the AEs must include severity, seriousness, relationship to study drug/IP, duration (dates of onset and resolution), and outcome.

In addition, the Investigator should report any AE or SAE they are made aware of that occurs after this time period and that is believed to have a reasonable possibility of being associated with study drug.

Diagnosis versus Signs and Symptoms

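### Appendix 3 defines a drug-causality judgement so that events caused only by study procedures also count as related, and Section 11.3 does not separate them again

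*Combined protocol and SAP*

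**What the plan says.** Under Assessment of Causality, Appendix 3 sets a drug-only task: "The Investigator will make a causality assessment about the relationship of each AE to study drug". The scale has two values: "The causal relationship of all AEs to the study drug will be judged as either related" or not related. The guideline that follows, introduced as a means of keeping assessments consistent, defines *related* as "at least a reasonable possibility that the event is caused by the study drug or the research procedures". The first limb of *not related* requires that no reasonable link is likely "between the event and study drug/IP or the research procedures".

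The paragraph on participation-emergent adverse events, also in Appendix 3, covers events arising from study participation or specimen collection. It says they are "noted as such in the case report form (CRF) as related to study intervention".

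Appendix 4, under Recording AEs and SAEs, lists what must be captured: "Details of the AEs must include severity, seriousness, relationship to study drug/IP, duration", and outcome. It says that events associated with protocol procedures are also collected, but names no item for relationship to procedure.

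Section 11.3 reports TEAEs, SAEs and AESIs "by severity, and by relationship to study drug, if applicable". It also gives the percentage of subjects with at least one treatment-related TEAE, SAE or AESI, without defining treatment-related. Separately, it plans summaries or listings, and narratives, for AEs related to study procedures.

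Section 8.3.3 has two criteria for notifying the DMC. The first counts relationship to study drug or study procedures; the second counts relationship to study drug only.

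**The concern.** The question put to the investigator is about the drug, but the rule for answering it is about the drug or the procedures. A site that follows the rule will answer yes for an event with no suspected drug cause, in a field labelled relationship to drug.

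This matters mainly because the Retreatment Period is single-arm and open-label. No concurrent control shows how often TEAEs would occur without setrusumab, so a reader will lean more than usual on the treatment-related percentages. If the field holds two different causes, those percentages no longer mean what their label says. With approximately 24 sites, it is also likely that some will follow the definition and others the drug-only lead sentence. The coding would then vary by site for reasons unrelated to the drug.

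**Working it through.** No arithmetic applies. The plan states no figure on this point and gives no count or rate of procedure-related events. The check is to follow one event through the text. Take a bruise from a study blood draw, with no suspected drug cause. The example is mine, but specimen collection is the procedure that Appendix 3 itself names.

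1. **Question asked (Appendix 3, Assessment of Causality).** Is the event related to study drug? On the plain wording, no.

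2. **Definition of related.** Is there a reasonable possibility that drug or procedures caused it? Yes, the procedures did. The event meets the definition.

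3. **Definition of not related.** The first limb fails, because a link to the procedures is likely. The second limb, joined by and/or, allows *not related* where another condition clearly caused the event. An investigator could stretch that to cover a blood draw, but the event would then meet both definitions. The text does not decide the case.

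4. **Listed criteria for related.** These are timing after IP, a known IP response, no explanation by disease, other illness or other therapy, dechallenge and rechallenge. They point to the drug and would lead many investigators to answer no. However, they describe when a drug link may exist; they do not cancel the wider definition above them.

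5. **Participation-emergent paragraph.** The bruise is to be noted as participation-related and also as related to study intervention. Tables 2 and 9 list setrusumab as the intervention. This pushes the answer back towards yes.

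6. **Recording (Appendix 4).** The required details include relationship to study drug/IP. No procedure item is named that would hold the other cause.

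7. **Analysis (Section 11.3).** A yes enters the tables by relationship to drug. If the onset follows the first dose, it can also enter the treatment-related TEAE percentage. Nothing removes it. The separate procedure-related output would show the event again, but showing it twice does not take it out of the treatment-related count.

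8. **DMC notification (Section 8.3.3).** A pooled yes fits the first criterion. It does not show whether the second, drug-only criterion is met.

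The direction is clear: compared with a drug-only item, the pooled definition can only add events to the related category. A subject-level percentage rises only through subjects who have no drug-related event of that class already.

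**The case against.** The strongest reply is that one stray phrase is being set against many drug-only statements. The lead sentence, the scale, the listed criteria, the Appendix 4 details and the Section 11.3 tables all refer to study drug or IP. Section 11.3 already plans separate output for procedure-related AEs, Appendix 3 has participation events noted as such, and Section 8.3.3 names the two causes separately. All of this presupposes that procedure attribution can be identified. The CRF is not among the documents and may already hold a separate item. Further safety-analysis detail is deferred to the SAP, and the text available contains no rule on this point. TEAEs are also summarised regardless of attribution, and a DMC reviews AESIs.

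Much of this stands. It rules out saying that the tables will be mixed. It does not remove the conflict, because the phrase sits in the operative definition and its mirror, and no text says which reading prevails. An analysis rule could not reliably separate two causes recorded in one answer.

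A reader might also infer three stronger things that the documents do not support:

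- **That a procedure-caused SAE becomes a suspected drug reaction.** The SUSAR definition in Appendix 3 requires a reasonable possibility of a causal link with study drug/IP and does not mention procedures.
- **That drug-free Observation Period events become treatment-related.** Table 3, footnote g, limits collection there to AESIs, which Section 10.6 assesses against prior setrusumab. Section 11.3 limits non-serious AEs in the analysis to onset after the first dose. Table 11 does start SAE collection at consent, but the point does not rest on that.
- **That the inflation can be quantified from the number of dosing visits.** This would need a per-visit rate of procedure events, and the documents offer no basis for one.

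**Conclusion.** The concern holds as an internal contradiction with a possible effect on analysis. The definition of *related* conflicts with the judgement it is meant to define. Read literally, it sends procedure-only events into the relationship-to-drug and treatment-related summaries, and it leaves a pooled answer that cannot serve both criteria in Section 8.3.3.

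A reader might infer that mixing happens by rule. The documents support less than that: the drug-only wording elsewhere may lead sites to code correctly, so mixing is a risk. Its direction is upward for the treatment-related counts; its size cannot be estimated from the documents.

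The conclusion assumes that some sites apply the definition as written, and that neither the CRF nor SAP text not seen here separates the two causes. If a separate procedure item already exists and the treatment-related tables use only the drug item, what remains is a wording correction in Appendix 3.

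**What to change.** - **Appendix 3, Assessment of Causality:** delete the reference to research procedures from the definitions of both *related* and *not related*, so that each concerns study drug only.
- **Appendix 3, participation-emergent events:** reword so that these events are noted as related to study procedure instead of study intervention.
- **CRF and Appendix 4:** record relationship to study procedure as its own item and add it to the required AE details. The procedure-related output already planned in Section 11.3 needs this item anyway.
- **Section 11.3:** state that treatment-related means related on the drug item only.

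Section 8.3.3 needs no change for this purpose: with two items, each criterion can be applied as worded. The cost is a few wording changes and one CRF item. No assessment, visit or clinical rule is affected.

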APPENDIX 4. ADVERSE EVENT COLLECTION, ELICITING, RECORDING AND REPORTING

Collection Period & Reporting Timeframe: Adverse Event & Other Safety Information Reporting

Table 11: Collection Period and Reporting Timeframes for Adverse Event and Other Safety Information Reporting

Event Type	Collection Period	Reporting Timeframe	Report to:
Serious Adverse Event (SAE)	Start: From the time the subject signs the ICF End: Two months after the final administration of study drug	Report all SAEs within 24 hours of site Investigator, designee or site personnel's knowledge of the event.	Electronic Data Capture (primary) Ultragenyx (back-up if Electronic Data Capture is down or not available) email: [contact] [contact]
Adverse Event (AE)	Start: From the time the subject signs the ICF End: Two months after the final administration of study drug	Report all non-serious AEs within a target of 3 business days of site Investigator, designee or site personnel's knowledge of the event.	Electronic Data Capture
Treatment- emergent adverse events (TEAEs)	Start: From the time the subject signs the ICF End: Two months after the final administration of study drug	Report all non-serious TEAEs within a target of 3 business days of site Investigator, designee or site personnel's knowledge of the event.	Electronic Data Capture
Pregnancy (includes Partner pregnancy)	Start: From the time the subject signs the ICF End: Two months after the final administration of study drug	Report all pregnancies within 24 hours of site Investigator, designee or site personnel's knowledge of the event	Electronic Data Capture (primary) Ultragenyx (back-up if Electronic Data Capture is down or not available) email: [contact] [contact]
Adverse Events of Special Interest (AESI)	Start: From the time the subject signs the ICF End: Two months after the final administration of study drug	Report all AESI within 24 hours of site Investigator, designee or site personnel's knowledge of the event.	Electronic Data Capture (primary) Ultragenyx (back-up if Electronic Data Capture is down or not available) email: [contact] [contact]

Table 12: Safety Contact Information

Global Drug Safety & Pharmacovigilance Serious Adverse Events, Adverse Events of Special Interest, and Pregnancy Reporting		Medical Monitor
Email: [contact]	PPD	, MD, MS
[contact]	PPD	
	PPD	

Eliciting Adverse Events

A consistent methodology of non-directive questioning for eliciting AEs at all patient evaluation time points should be adopted. Examples of non-directive questions include:

- "Since the last visit, has the patient experienced any health problems?"
- "Have there been any new or changed health problems since you were last here?"

Recording AEs and SAEs

All AEs (ie, any new condition or worsening in severity or frequency of a preexisting condition) experienced by the patient within the protocol defined timeframes must be promptly documented on the case report form (CRF) and SAE form if applicable. For clinically significant worsening of a preexisting condition from Baseline the changes will be documented as AEs on the CRF. Clinical significance is defined as any variation in signs, symptoms, or testing that has medical relevance and may result in an alteration in medical care. The Investigator will continue to monitor the patient until the assessment returns to Baseline or until the Investigator determines that follow-up is no longer medically necessary.

For IP and for non-IP studies, any AEs or SAEs considered associated with study protocol-required procedures will also be collected

The Investigator is responsible for evaluating all AEs, obtaining supporting documents, and ensuring documentation of the events is adequate. Details of the AEs must include severity, seriousness, relationship to study drug/IP, duration (dates of onset and resolution), and outcome.

In addition, the Investigator should report any AE or SAE they are made aware of that occurs after this time period and that is believed to have a reasonable possibility of being associated with study drug.

Diagnosis versus Signs and Symptoms

If known, a diagnosis should be recorded on the CRF and SAE form (if applicable) rather than individual signs and symptoms. Whenever medically appropriate, the Investigator should group signs or symptoms that constitute a single diagnosis into a unifying event term. For example, record "liver failure" rather than jaundice, asterixis, and elevated transaminases, or record "upper respiratory tract infection" rather than cough, rhinitis, and sneezing. However, if a constellation of signs and/or symptoms cannot be medically characterized as a single diagnosis or syndrome at the time of reporting, each individual event should be recorded as an AE on the CRF and SAE form (if applicable). If a diagnosis is subsequently established, it should be reported as follow-up information by revising the CRF and SAE form (if applicable). Vague, nonspecific AE terms such as "erythema," "rash," or "lump on head" should be avoided and more specific information

should be provided, such as "erythematous macule on right leg," "allergic dermatitis," or "scalp cyst."

Adverse Events Occurring Secondary to Other Events

In general, AEs occurring secondary to other events (eg, cascade events or clinical sequelae) should be identified by their primary cause. For example, if severe diarrhea is known to have resulted in dehydration, it is sufficient to record only diarrhea as the AE on the CRF and, if also serious, on the SAE form. However, medically significant AEs occurring secondary to an initiating event that are separated in time should be recorded as independent events on the CRF. For example, if a severe gastrointestinal hemorrhage leads to renal failure, both events should be recorded separately on the CRF.

Persistent or Recurrent Adverse Events

A persistent AE is one that extends continuously, without resolution between patient evaluation time points. Such events should only be recorded once in the CRF unless their severity increases. If a persistent AE becomes more severe, it should be recorded again on the CRF.

A recurrent AE is one that occurs and resolves between patient evaluation time points and subsequently recurs. All recurrent AEs should be recorded individually on the CRF.

Abnormal Laboratory Values

Only clinically significant laboratory abnormalities in the opinion of the Investigator are to be recorded as AEs on the CRF and SAE form (if applicable). For example, abnormalities that require study drug dose modification, discontinuation of study drug, more frequent follow-up assessments, or further diagnostic investigation may be considered clinically significant by the Investigator.

If the clinical significant laboratory abnormality is a sign of a disease or syndrome (eg, alkaline phosphatase and bilirubin 5 × upper limit of normal associated with cholecystitis), only the diagnosis (eg, cholecystitis) needs to be recorded on the CRF and the SAE form (if applicable).

If the laboratory abnormality can be characterized by a precise clinical term, the clinical term should be recorded as the AE or SAE. For example, an elevated serum potassium level of 7.0 mEq/L should be recorded as "hyperkalemia."

Observations of the same clinically significant laboratory abnormality from visit to visit should not be repeatedly recorded as AEs on the CRF and SAE form (if applicable), unless their severity, seriousness, or etiology changes.

Reporting Serious Adverse Events

Any AE that meets SAE criteria must be reported to Ultragenyx or its designee within 24 hours of the site Investigator, designee or site personnel's knowledge of the event. Regardless of causality, all SAEs must be reported during the time period specified. All SAEs must also be recorded in the patient's source documentation and on the CRF. Copies of discharge summaries, consultant reports, and any other relevant documents should be provided with the SAE report when available.

If follow-up is obtained or requested by Ultragenyx and/or the Medical Monitor, the additional information should be sent within 24 hours of knowledge.

Refer to Safety Contact Information for SAE reporting.

Reporting of Pregnancy in Subject or Partner

For protocols requiring pregnancy reporting, any reported pregnancy of a subject or a subject's partner that occurs during participation in the study will be monitored for the full duration of the study and/or followed until the outcome of the pregnancy is known. In the event of a pregnancy in the partner of a subject, the Investigator should make every effort to obtain the female partner's consent for release of protected health information.

Pregnancy in a subject or subject's partner, complications of the pregnancy and the outcomes of pregnancy should be reported to the Ultragenyx or designee within 24 hours of site Investigator, designee or site personnel's knowledge of the event.

Pregnancies will be reported by completing and submitting Pregnancy Notification Form to Ultragenyx or designee.

Pregnancy outcomes will be reported by completing and submitting Pregnancy Outcome Form to Ultragenyx or designee.

The following pregnancy outcomes should always be classified as serious and reported to Ultragenyx or designee within 24 hours by completing and submitting the SAE and Pregnancy Outcome Form:

- Spontaneous abortion/Miscarriage
- Therapeutic abortion
- Ectopic pregnancy
- Fetal death/Still birth
- Molar pregnancy
- Birth defect/Congenital anomaly

Reporting Suspected Unexpected Serious Adverse Reactions

Ultragenyx or its designee will submit suspected unexpected serious adverse reactions (SUSARs) to appropriate Regulatory Authorities (including Competent Authorities in all Member States concerned), Institutional Review Boards /Independent Ethics Committees (IRBs/IECs), and Investigators as per local laws and regulations. Fatal and life-threatening SUSARs will be submitted no later than seven calendar days of first knowledge of the event and follow-up information submitted within an additional eight days. All other SUSARs will be submitted within 15 calendar days of first knowledge of the event.

The Investigator will notify the IRBs/IECs of SUSAR, in accordance with IRB/IEC requirements and local laws and regulations.

Non-SUSARs will be maintained in the Ultragenyx global safety database and provided in annual safety reports and/or other aggregate periodic summary reports to Regulatory Authorities and IRBs/IECs per local laws and regulations.

Reporting Urgent Safety Measures

Investigators are required to report any urgent safety measures taken to protect the safety or welfare of subject to Ultragenyx or its designee within 24 hours. Ultragenyx or its designee will inform the Regulatory Authorities, IRBs/IECs, and other investigators of any events (eg, change to the safety profile of Investigational Product (IP), major safety findings) that may occur during the clinical study that do not fall within the definition of a SUSAR but may affect the safety of subjects participating in the clinical study, as required, in accordance with applicable laws and regulations.

The Investigator will notify the IRBs/IECs of urgent safety measures, in accordance with IRB/IEC requirements and local laws and regulations.

